2.7 Timing of Outcome Assessments

For all clinically planned measures, visits should occur within a window of the scheduled visit. Visits outside visit window is regarded a protocol deviation. The target day and visits window are defined in the protocol as:

Visit Label	Target Day	Definition (Day window)
Diagnosis	-1	Prior to Day 0
V1. Baseline	Day 0 (Randomization)	Day 0
V2. Surgery/Casting	Day 1	< 8 days from injury
V2. 2 weeks	14 days from casting	Target day \pm 7 days
V3. 4 weeks	28 days from casting	Target day \pm 7 days
V4. 8 weeks	56 days from casting	Target day \pm 14 days
V5. 3 months	91 days from casting	Target day \pm 30 days
V6. 6 months	182 days from casting	Target day \pm 30 days
Last study visit*	364 days from casting	334 to 728

*The patients are physically tested by a physiotherapist at 1-2 years. Most often they are asked to complete the PROMs prior to the testing, either by link send by e-mail, on site on a tablet, or on paper when a tablet is not present or online. Some patients did not show up for the 1-2 years testing but did complete the PROMs. Some patients showed up for testing at 1-2 years but did not complete the questionnaires. The last study visit is defined as the last of either the 1-2 years test day or completion of the 1-2 years PROMs.

STATISTICAL ANALYSIS PLAN for the Achilles trial

For analysis and tabulation purposes, we define study time points as

Time Point Label	Target Day	Definition (Day window)
TP1. Baseline	Day 0 (Randomisation)	Information up to randomisation + 14 days
TP2. Month 3	91	Days 61 to 121
TP3. Month 6	182	Days 151 to 212
TP4. Year 1-2	364	Days 334 to 728

3 Statistical Principles

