For each of these endpoints, a similar measurement for the healthy Achilles is performed. The ratio of the test result in the treated foot versus the healthy foot is calculated and multiplied with 100. This measurement is referred to as the Limb symmetry index (LSI). These are also considered as secondary endpoints. Furthermore, the physical tests are performed both at the 6-month visit and at the 1-2 years visit, the results of which are both considered as secondary endpoints. Furthermore, the change in the test results, from the 6-month to the 1-2 years visit, are also considered secondary endpoints. Thus, there are 36 secondary endpoints relating to the physical tests.

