5.2.4.1 Main Analysis

There are three outcomes for each physical test:

- The difference between the 6-month and the 1-2 years test performance.
- The 6-month test performance.

STATISTICAL ANALYSIS PLAN for the Achilles trial

- The 1-2-year test performance.

Linear regression models will be fitted to each of these outcomes, for each physical test. The treatment variable will be adjusted by study centre (the stratification variable used in the randomization). Note that for each of the 6 physical tests at each visit, a test is also performed in the healthy foot. The ratio between the performance in the treated foot and the healthy foot, multiplied with 100, (the LSI) is also considered an outcome variable for each physical test.

The analyses will be conducted in the FAS.

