5.2.4.2 Summary Measures

The effect estimates will be the pairwise differences in the estimated marginal means (that is, mean difference adjusted for study centre) between the treatment groups, reported together with 95% confidence intervals.

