5.2.4.4 Missing Data

We expect three types of missing data for these outcome variables:

1. Individuals is present in the gym, tries to perform the test, but do not manage to fulfil the minimum requirements to have the test approved. These values are in reality censored rather than missing.
2. Value may be missing due to e.g. non-working equipment in the gym where the test takes place, even if the patient were physically there.
3. Values may be missing because the patient did not show up for the physical tests.

The following handling of the three types of missingness will be performed:

1. Threshold imputation: These values will be imputed in the following way:
 - I. The 1% highest and 1% lowest observed values for the variable will be removed, and a normal distribution will be fitted to the 'trimmed' observations.
 - II. Values "klarte ikke" (did not manage) will be replaced by drawing values from the distribution in point I, truncated by 0 and the 10th percentile of the distribution.
2. These values are assumed to be missing at random, and multiple imputation by chained equation will be performed.
3. Multiple imputation using chained equations will be used to impute these values.

The multiple imputation in point 2 and 3 will be done simultaneously, after point 1 has been performed. The following variables will be used to impute the test scores at 6 months and 1-2 years: Sex, Age, Weight at baseline, weight at the time of the test, study centre, results in the other 5 physical tests, results from all 6 physical test in the healthy foot, and ATRS scores at 6 and 1-2 years.

STATISTICAL ANALYSIS PLAN for the Achilles trial

Note that the LSI variables, which is the ratio between the injured and the healthy foot multiplied by 100, will not be imputed as described above. For the threshold imputation, the value in the injured and healthy foot will be imputed separately, and the LSI value is obtained from these. In the multiple imputation procedure, the LSI variables for the different tests will be imputed by passive imputation.

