5.2.4.5 Sensitivity Analyses

Performing the analysis described in Section 5.2.4.1 on the population of patients that showed up for the physical test. I. e. after the threshold imputation described in Section 5.2.4.4 has been performed.

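### The imputation variables listed for the physical tests leave out randomised arm, so the between-arm estimates can be biased, usually toward no difference

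*SAP*

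**What the plan says.** SAP 5.2.4.4 separates three kinds of missing physical-test value: an attempted test that was not achieved (handled by threshold imputation), equipment failure, and non-attendance, described as "Values may be missing because the patient did not show up for the physical tests". The second and third are filled together by chained-equation multiple imputation, from a stated list of predictors. The list begins "The following variables will be used to impute the test scores at 6 months and 1-2 years: Sex, Age, Weight at baseline" and goes on to "weight at the time of the test, study centre, results in the other 5 physical tests", then the healthy-foot tests and ATRS at 6 months and 1-2 years. Treatment arm does not appear, and no section says that the imputation is run by arm.

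The analysis in 5.2.4.1 is a linear regression in the full analysis set: "The treatment variable will be adjusted by study centre (the stratification variable used in the randomization"). Under 5.2.4.2, "The effect estimates will be the pairwise differences in the estimated marginal means", with 95% confidence intervals. Section 5.1.3.4 counts 36 endpoints of this kind and adds that "the change in the test results, from the 6-month to the 1-2 years visit, are also considered secondary endpoints". The one sensitivity analysis, in 5.2.4.5, is run "on the population of patients that showed up for the physical test".

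**The concern.** The variable whose effect the regression estimates is the one left out of the model that fills in the outcome. Two patients with the same centre, weights, ATRS and other results receive imputed values from the same distribution whatever arm they were in. Any effect of treatment on the test that those predictors do not reflect is therefore absent from the imputed part of the data, and the pooled estimate mixes a correct observed part with a diluted imputed part.

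The reverse is also possible. If ATRS or the other tests differ more between arms than the test being imputed, the imputed values import a difference that is too large, or one that does not exist.

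No-shows are the more exposed group, because the whole battery at that visit is normally absent and ATRS becomes the main same-visit predictor. Section 2.7 confirms that it is sometimes available: "Some patients did not show up for the 1-2 years testing but did complete the PROMs". At stake are the reported between-arm differences for a named secondary objective.

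**Working it through.** **The plan's own figures.** The SAP states no figure for this imputation: no missing fraction, arm effect or correlation for the physical tests. Two planning figures are borrowed from 2.3 to set a scale. A one-way ANOVA with means 0, 3.5 and 7, SD 20 and 160 per arm gives power 0.804, so the planned 480 reproduces. The borrowed values are an effect of 7/20 = 0.35 SD and a loss of (530 − 480)/530 = 9.4%. Both were set for ATRS, not for these tests.

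**Formula.** With missing fraction p, true arm effect d on the test, and transmitted effect t (the sum over predictors of imputation coefficient × arm effect on that predictor), values missing completely at random and arm omitted:

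bias ≈ −p × (d − t); share retained ≈ 1 − p × (1 − t/d).

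**Assumed correlations (unit SD).** Different tests at the same visit 0.5; same test across visits 0.6; different tests across visits 0.4; ATRS with a test 0.4 at the same visit and 0.3 at the other; ATRS across visits 0.6.

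**Coefficient sums.** For two ATRS scores: (0.4 + 0.3)/(1 + 0.6) = 0.44. For the other five tests at the same visit plus both ATRS scores: 0.87. For the other five tests at 6 months plus both ATRS scores: 0.77, of which the tests contribute 0.60. If the test's own 6-month result is added: 0.83, of which the tests contribute 0.70. When every predictor carries the same standardised effect as the test, t/d equals the sum. When ATRS carries none, t/d equals the tests' part.

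**Share of the true effect retained, from the formula**

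| Scenario | t/d | p = 9.4% | 20% | 30% |
|---|---|---|---|---|
| No-show, nothing transmitted | 0 | 91% | 80% | 70% |
| No-show, ATRS only, same effect | 0.44 | 95% | 89% | 83% |
| No-show, ATRS + other five 6-month tests, ATRS carries the effect | 0.77 | 98% | 96% | 93% |
| As above, ATRS carries no effect | 0.60 | 96% | 92% | 88% |
| No-show, own 6-month test also in, ATRS carries the effect | 0.83 | 98% | 97% | 95% |
| As above, ATRS carries no effect | 0.70 | 97% | 94% | 91% |
| Equipment failure, other tests and ATRS share the full effect | 0.87 | 99% | 97% | 96% |

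Example: no-show, ATRS only, 20% missing: 1 − 0.20 × (1 − 0.44) = 0.89.

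**Simulation.** The set-up was 160 per arm, one arm shifted, 20 imputations, Rubin's rules and 1,500–2,000 replicates. With arm omitted, it retained 90/79/69% where nothing is transmitted, 96/89/85% with ATRS only, and 99/98/97% for equipment failure, at 9.4/20/30% missing. If the other tests and ATRS share only half the effect, equipment failure retains 95/89/83%. With arm in the imputation model, every estimate was within 0.007 SD of the truth. A separate simulation with 176 per arm and a single composite predictor gave the same pattern at 20% missing: about −20% with nothing transmitted, and −15% to −7% when the predictor shares the effect (correlation 0.3 to 0.6).

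**Opposite direction.** For equipment failure with no true effect on the test and 0.35 SD on the predictors, t = 0.87 × 0.35 = 0.305, so the bias is +0.029, +0.061 and +0.091 SD at the three fractions (simulated 0.028/0.060/0.091). For no-shows with ATRS at 0.35 SD and no test effect, the simulated estimate was 0.012/0.030/0.042 SD.

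**Change from 6 months to 1-2 years.** There are 6 tests × 2 (raw and limb symmetry index) = 12 such endpoints among the 36. Suppose 0.35 SD at both visits, so a true difference in change of 0, with no-shows at the later visit only. The simulated estimate is −0.032/−0.070/−0.102 SD if ATRS carries no effect, −0.021/−0.036/−0.057 if it carries the same effect, and −0.004/−0.014/−0.015 if 6-month tests also enter. Here the bias creates a difference rather than shrinking one.

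**Not covered.** The limb symmetry index endpoints, half of the 36, are imputed passively and were not simulated. Threshold imputation of failed tests is a separate procedure and is not part of this point.

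**The case against.** One defence is that the list names auxiliary variables only and that the analysis-model variables go in as a matter of course. The text does not support that: study centre, the other term in the analysis model, is listed, so a programmer following the list would leave arm out.

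Other objections do stand.

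- Bias is not inevitable. It vanishes when the predictors transmit exactly the test's effect, including when there is no arm effect anywhere. A reader might infer that the physical-test estimates are certainly wrong; the document shows only that they can be.
- The lower no-show figures suppose that nothing useful is available. The list does not restrict the other tests to the same visit, so someone absent only at 1-2 years may have 6-month results in the model, and the loss is then modest.
- All scenarios here are missing completely at random. Under that condition the attenders-only analysis in 5.2.4.5 is unbiased for these two kinds of missingness, so the report would hold an unaffected estimate beside the main one. It need not be unbiased under weaker assumptions, and it does not repair the main analysis.
- Simulated coverage of the 95% intervals with arm omitted stayed between 0.925 and 0.984. The harm is a shifted estimate, not a collapse of coverage.

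A reader might also infer that the trial's main conclusion is in doubt. It is not: the primary ATRS analysis does not use this imputation, and 2.4.1 treats all tests outside the two-step primary procedure as supportive or exploratory.

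**Conclusion.** Wrong as written. The predictor list is definite, includes centre and omits arm, while the analysis estimates arm differences. The direction is usually toward no difference but is not guaranteed, and it can go either way for the change endpoints.

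The size cannot be stated for this trial. The percentages are scenarios that rest on a borrowed 0.35 SD effect, assumed correlations and assumed missing fractions. A loss of 20–30% of one test to equipment would be extreme. At about 9% missing, the loss is at most about a tenth of the effect in the no-show scenarios. It approaches a third only at 30% missing with predictors that transmit nothing. The case for changing the plan rests on a clear defect with a very cheap remedy, not on demonstrated large harm.

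**What to change.** In SAP 5.2.4.4, add randomised treatment arm to the imputation variables for equipment failure and non-attendance, or state that imputation is done separately within each randomised arm. The cost is one line of text and one three-level predictor in the imputation code. No new data are needed, and the primary analysis does not change.

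### The imputation list for the physical tests leaves out the injured foot's result on the same test at the other visit, which weakens the between-visit link and inflates the variance of the change endpoints

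*SAP*

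**What the plan says.** SAP 5.1.3.4 states that "the change in the test results, from the 6-month to the 1-2 years visit, are also considered secondary endpoints". SAP 5.2.4.1 lists as one of three outcomes per test: "The difference between the 6-month and the 1-2 years test performance". Under 5.2.4.2, "The effect estimates will be the pairwise differences in the estimated marginal means" between treatment groups, adjusted for centre.

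SAP 5.2.4.4 distinguishes three kinds of missing test value: attempted but not achieved (threshold imputation), equipment failure, and non-attendance. The last two are imputed by chained equations: "The multiple imputation in point 2 and 3 will be done simultaneously, after point 1 has been performed". For equipment failure it adds: "These values are assumed to be missing at random, and multiple imputation by chained equation will be performed". It states no such assumption for non-attendance.

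The predictors are introduced by "The following variables will be used to impute the test scores at 6 months and 1-2 years". They are "Sex, Age, Weight at baseline, weight at the time of the test, study centre", followed by "results in the other 5 physical tests, results from all 6 physical test in the healthy foot, and ATRS scores at 6 and 1-2 years".

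**The concern.** The list gives five tests for the injured foot, six for the healthy foot, and both visits for ATRS. Read literally, a missing injured-foot value is imputed without that foot's own result on the same test at the other visit. No other section adds it.

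For a patient tested at one visit only, the omitted value is probably the strongest single predictor available. It is also one of the two terms of the change endpoint. The change becomes an observed value set against an imputed value that was drawn without reference to it. The imputation model therefore does not match the analysis it feeds. Two things are at stake: the precision of the change endpoints and, if attendance at 1-2 years depends on how the patient did at 6 months, the mean change within each arm.

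**Working it through.** **Endpoints affected.** The plan's count is 36. It reproduces as 6 tests × 2 scales (raw, LSI) × 3 outcomes (6 months, 1-2 years, change) = 36. The change endpoints are 6 × 2 = 12.

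**Inputs.** The SAP gives no between-visit correlation, explained variance or missing rate for these tests. The sample-size figures in 2.3 concern ATRS and do not enter. All of the following are therefore assumptions:
- r, the correlation of the same test between visits: 0.7 to 0.9.
- R², the share of variance that the listed variables explain at each visit, through the same combination: 0.5 to 0.6.
- f, the share of patients with one visit imputed: 20%, with 10% shown for comparison.
- Equal variance at both visits, set to 1.

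**Variance of the change for a patient with one visit imputed.**
- True value: 2 − 2r.
- Imputed from the list as written, the covariance falls from r to R², so the variance is 2 − 2R².
- Ratio k = (2 − 2R²)/(2 − 2r).
- SD of change over all patients, relative to the truth: √((1 − f) + f·k).

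| r | R² | True variance | As written | k | SD excess, f = 20% | SD excess, f = 10% |
|---|---|---|---|---|---|---|
| 0.7 | 0.6 | 0.6 | 0.8 | 1.33 | 3.3% | 1.7% |
| 0.7 | 0.5 | 0.6 | 1.0 | 1.67 | 6.5% | 3.3% |
| 0.8 | 0.6 | 0.4 | 0.8 | 2.0 | 9.5% | 4.9% |
| 0.8 | 0.5 | 0.4 | 1.0 | 2.5 | 14.0% | 7.2% |
| 0.9 | 0.6 | 0.2 | 0.8 | 4.0 | 26.5% | 14.0% |
| 0.9 | 0.5 | 0.2 | 1.0 | 5.0 | 34.2% | 18.3% |

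Example, r = 0.8, R² = 0.5, f = 0.2: √(0.8 + 0.2 × 2.5) = √1.3 = 1.14.

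**Check by simulation** (400,000 standardised patients, 20% of 1-2-year values missing completely at random, r = 0.7, R² = 0.5). Among imputed patients the between-visit correlation was 0.496 with the list as written and 0.697 with the 6-month value added, against a true 0.700. The variance of change was 1.000 and 0.603 respectively, against a true 0.597. The mean change was unbiased either way.

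**Bias in the mean when absence depends on the 6-month result** (logistic missingness, about 22% missing). The pooled mean change was too high by 0.061 SD at r = 0.8, R² = 0.5; by 0.042 at 0.8, 0.6; and by 0.062 at 0.9, 0.6. In a separate run targeting 20% missing at an average 6-month score, it was 0.022 at r = 0.6, R² = 0.5. With the 6-month value added it was within about 0.003 SD of zero. Weaker predictors make it worse: about 0.13 SD at r = 0.8, R² = 0.2.

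**Bias in the contrast that the plan reports** (two arms, same missingness model).
- Arms with equal scores: 0.001 SD or less.
- Arms 0.3 SD apart at both visits, r = 0.8, R² = 0.5: −0.068 SD with the list as written, −0.011 with treatment arm alone added, and −0.023 with the 6-month value alone added. Most of this distortion comes from the absence of treatment arm from the same list, which is a separate point. About 0.01 SD remains attributable to the present omission once arm is included.

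**The case against.** A reader might infer that the imputation breaks the link between visits, or that the treatment comparisons are biased by 0.04 to 0.06 SD. The document supports neither. The listed variables preserve part of the association (0.5 to 0.6 in the table, against a true 0.7 to 0.9), so the link is attenuated. The 0.04 to 0.06 SD is bias in a pooled mean, whereas 5.2.4.2 reports pairwise differences between arms, where it largely cancels when scores and missingness are alike.

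The other objections carry some weight:
- **The size rests on inputs from outside the plan.** 5.2.4.4 does not say at which visit the other five tests and the healthy-foot results enter. If both visits enter, R² could exceed 0.6. At r = 0.8 and R² = 0.7 the SD excess is only 4.9% with 20% imputed and 2.5% with 10%. On the other hand, a patient who did not attend lacks all six tests in both feet, and the weight, for that visit. If the list is read as same-visit only, little is left beyond sex, age, baseline weight, centre and ATRS.
- **Selective absence is conjecture.** Nothing in the SAP says that poor performers at 6 months skip the later test. Failed attempts are handled separately and equipment faults have no evident link with performance, so only non-attendance could follow that pattern.
- **There is a partial safeguard.** The sensitivity analysis in 5.2.4.5 uses only patients who attended, so non-attenders are not imputed. It neither repairs the main analysis nor adjusts for selective attendance.
- **Software may include the variable by default.** A wide-format run could do so, but an analyst who follows the stated list would leave it out. If inclusion is intended, the text needs the same correction.

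**Conclusion.** The omission stands on the text, and it weakens the analysis of the 12 change endpoints. The firm consequence is inflated variance and lost precision: an SD of change roughly 3% to 34% too large over the assumed ranges with 20% imputed, and less if fewer values are imputed or the listed variables explain more. Bias of about 0.02 to 0.06 SD in the arm-level mean change is conditional on absence depending on the 6-month result. For the between-arm contrasts it is close to zero when arms are similar. With arms 0.3 SD apart it is about 0.01 SD once treatment arm is in the imputation model.

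The imputed scores at each visit also lose information, but the change endpoints are affected most directly. All of these are secondary endpoints that SAP 2.4.1 treats as supportive or exploratory. The primary ATRS analysis and the re-rupture analysis are untouched. The point merits correction because the remedy is cheap and uses data already collected.

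**What to change.** In SAP 5.2.4.4, state that both visits are imputed jointly in wide format. Add the same test's injured-foot and healthy-foot results at the other visit to the predictors, and say at which visits the other tests enter. Derive the change and the LSI passively from the completed scores. Add treatment arm in the same edit; it is a separate point, but the two corrections belong together.

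The cost is a sentence in the SAP and a revised predictor matrix, with no new data. The downside is a larger imputation model with more collinear predictors, which needs convergence checks and possibly some pruning of weak terms, keeping the other-visit result and treatment arm.

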5.2.4.3 Assumption Checks

Visual inspection of residual plots will be performed (qq-plots, histograms and residuals vs. fitted values). Substantial deviations from normality will be addressed by suitable transformations of the data.

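### Forming LSI from separate threshold draws that reach down to 0 makes it unstable when the healthy foot fails, and the draw is undefined if the fitted 10th percentile is at or below 0

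*SAP*

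**What the plan says.** SAP Section 5.1.3.4 defines LSI with the healthy foot as denominator: "The ratio of the test result in the treated foot versus the healthy foot is calculated and multiplied with 100". It counts 36 physical-test endpoints: 6 tests, each as an absolute value and as LSI, at 6 months, at 1-2 years and as the change between them (6 × 2 × 3). LSI therefore supplies 18 of the 36.

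Section 5.2.4.4 separates failed attempts from absent patients and broken equipment. Of the failures it says "These values are in reality censored rather than missing". After the top and bottom 1% of observed values are removed, "a normal distribution will be fitted to the 'trimmed' observations", and each failure is replaced by "drawing values from the distribution in point I, truncated by 0 and the 10th percentile of the distribution". For LSI, "the value in the injured and healthy foot will be imputed separately, and the LSI value is obtained from these". The SAP thus provides for a failed healthy foot. It gives no lower limit above 0, no link between the two draws of one patient, no bound on LSI, and no rule for a 10th percentile at or below 0.

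Section 5.2.4.1 states: "Linear regression models will be fitted to each of these outcomes, for each physical test". Section 5.2.4.2 reports differences in centre-adjusted means.

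**The concern.** A draw near 0 does little harm in a numerator, where it gives a low LSI. In a denominator it gives an LSI of several hundred or several thousand. A least-squares comparison of means gives such a value full weight, so one or two artificial ratios can inflate an arm's SD and pull its mean. This would happen in the patients about whose symmetry least is known.

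There is a separate gap in the definition. The upper limit is the 10th percentile of the fitted normal, which need not be positive. If it is not, the programmer has no interval to draw from and must improvise, possibly after seeing the data.

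**Working it through.** **Inputs from the SAP.** Truncation limits, separate draws, the LSI ratio and the linear model are as above; 160 per arm comes from Section 2.3. The SAP states no figure of its own on this point, so there is none to reproduce.

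**Assumptions, because the SAP gives no values.** CV of 0.2 to 0.6, the same in both feet; injured-foot mean equal to, or 80% of, the healthy-foot mean; true LSI SD of 20; 1%, 2% or 5% of an arm failing both feet.

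**1. When the interval exists.** The fitted 10th percentile is mean − 1.2816 × SD = mean × (1 − 1.2816 × CV). It is positive only if CV < 1/1.2816 = 0.780. At CV 0.4 it is 1 − 0.513 = 0.487 of the mean; at CV 0.8 it is 1 − 1.025 = −0.025, and no draw is possible.

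**2. No finite mean.** Let H be the healthy-foot draw, with density f on (0, q). Then E(1/H) = ∫ f(h)/h dh from 0 to q. Because f is positive at 0, the integral diverges. The injured-foot draw is independent of H, so E(LSI) is infinite too. This is true at every CV but matters little when CV is small, because almost no mass then lies near 0.

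**3. Size for a failed patient.** One million truncated-normal draws per foot and CV; LSI = 100 × injured/healthy. The equal-means column comes from repeat simulations of the same kind.

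| CV | Fitted 10th percentile (× mean) | Healthy draws below 10% of mean | Both failed, equal means: LSI > 500 | Both failed, injured mean 80%: LSI > 500 | Healthy only failed: median LSI |
|---|---|---|---|---|---|
| 0.2 | 0.744 | 0.0% | about 0% | about 0% | 119 |
| 0.3 | 0.616 | 0.9% | 1% | 1% | 158 |
| 0.4 | 0.487 | 6.4% | 4% | 3% | 226 |
| 0.5 | 0.359 | 17% | 7% | 5% | 351 |
| 0.6 | 0.231 | 36% | 8% | 7% | 608 |

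In the last column the injured foot scores 80% of the healthy mean. The lowest attainable LSI there is 80 divided by the second column: 80/0.744 = 108 at CV 0.2 and 80/0.359 = 223 at CV 0.5.

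**4. Size for an arm of 160 (true SD 20, equal means).**
- 5% failing both feet (0.05 × 160 = 8 patients): median arm SD about 20 / 22 / 26 / 35 / 40 at CV 0.2 / 0.3 / 0.4 / 0.5 / 0.6. Heavy tails make this vary between simulation runs: 26 to 28 at CV 0.4, 40 to 45 at CV 0.6.
- 2% failing: median 22 to 23 at CV 0.4 to 0.6, but one arm in ten exceeds about 43 to 45 / 76 to 79 / 85 to 109 at CV 0.4 / 0.5 / 0.6.
- 1% failing: median near 20 to 21, with the upper tail inflated from CV 0.4.
- 5% failing with the injured mean at 80%: median about 24 / 30 / 35 at CV 0.4 / 0.5 / 0.6.

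**5. Effect on a contrast.** The half-width of a 95% interval for a two-arm difference is 1.96 × SD × √(2/160). With SD 20 in both arms it is 1.96 × 20 × 0.1118 = 4.4 LSI points; with SD 35 it is 1.96 × 35 × 0.1118 = 7.7.

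**The case against.** The strongest reply is that this may never matter. A truncated normal piles up towards its upper limit, so a failed healthy foot need not give a near-zero denominator: at CV 0.2 to 0.3 hardly any draw falls below 10% of the mean and the arm SD barely moves. Healthy feet may rarely fail. All of this stands, and it is why the full CV range is shown.

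It can also be said that the SAP has a remedy: "Substantial deviations from normality will be addressed by suitable transformations of the data". An LSI of 500 would show on a residual plot. But the transformation is unspecified, would be chosen after seeing the data, and leaves the imputation limits as they are. The sensitivity analysis in Section 5.2.4.5 runs after the same threshold imputation, so it carries the same values.

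Three stronger readings are not supported:
- **That the interval is empty for skewed tests.** The condition is a fitted CV of at least 0.78, not skewness. A gamma with shape 2 (skew 1.4, trimmed CV 0.66) and a lognormal with sigma 0.7 (skew 2.9, trimmed CV 0.69) both leave a valid interval; an exponential (trimmed CV 0.92) does not. Nothing in the SAP shows that any test reaches 0.78.
- **That every LSI contrast is distorted.** Each would need healthy-foot failures in that test, at that visit, with a large enough CV.
- **That failing on both feet ought to give a poor LSI.** LSI measures symmetry. With both feet failed the imputed median is simply the ratio of the foot means (about 80 if the injured mean is 80% of healthy); the fault lies in the spread.

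**Conclusion.** The point holds as a defect of the rule. With a failed healthy foot, LSI can be extreme and has no finite mean while means are what is compared, and the draw is undefined at a fitted CV of 0.78 or more. The mechanism follows from the SAP text; the size rests on assumed CVs, foot means and failure rates. It is negligible at CV 0.2, modest at 0.3 and material from about 0.4 if several patients per arm fail on the healthy foot. At 1% failing both feet the typical arm is unaffected and the risk lies in an occasional badly inflated one. The 18 LSI endpoints are secondary, and Section 2.4.1 treats every test outside the two-step ATRS procedure as supportive or exploratory, so the primary conclusion is not touched. The change is still worth making, because the rule can give a wrong result and is cheap to repair.

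**What to change.** In Section 5.2.4.4:
- Do not derive LSI from a threshold-imputed healthy-foot value. When the healthy foot failed, exclude LSI for that test and visit (and the change that uses it) from the main LSI analysis, and report the number excluded by arm.
- Leave the absolute injured-foot endpoints as planned.
- Add a sensitivity analysis that keeps these patients with a bounded LSI, the bound being fixed before the data are analysed by arm.
- For the remaining threshold draws, use the empirical 10th percentile of the observed values as the upper limit in place of "truncated by 0 and the 10th percentile of the distribution". It is positive whenever the observed values are, so the interval always exists.

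Imputing the excluded LSI as ordinary missing data is not a good substitute, because it discards the known failure.

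The cost is a few lines of text and code, one extra sensitivity analysis, and a few patients lost from the LSI analysis. An injured-foot failure in those patients is still captured in the absolute endpoints.
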